## 9 Data and Safety Monitoring Plan

### 9.2 Periodic evaluation of data

All game events will be monitored for the possibility of adverse reactions to the game experience (the only study intervention).

### 9.3 Data that are reviewed

Adverse reactions (e.g. emotional distress) experienced by player participants.

### 9.4 Method of collection of safety information

Direct observation

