## 1.2 Primary Study Endpoints

Successful completion of data collection of 800 participants (400 players and 400 spokespersons) who play the "Who Would You Choose" game.

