## 7.0 Study Design and Procedures

## 7.1 Study Design

This study will use a convergent mixed methods design to: 1) explore how playing the serious game, “Who Would You Choose” (WWYC), affects individuals’ choice of a spokesperson; 2) establish the feasibility of using WWYC for helping people designate an appropriate spokesperson for healthcare decisions and 3) receive a positive response from the spokesperson which will be confirmed with a completed REDCap survey. In each game event (lasting ~2 hours), research staff will help facilitate game-play for groups of 4 players, who will also 1) complete baseline questionnaires, 2) complete post-game questionnaires, and 3) participate in post-game focus group discussions. Then, players will use text messages initiated by the associated WWYC smartphone App to engage their chosen spokespersons by sending a text message inviting them to complete a brief REDCap survey asking what medical preferences they think the player would want in various clinical scenarios. If this spokesperson does not respond or complete the survey within one week, the player may forward the same test message with REDCap survey link to an alternate spokesperson. If the alternate spokesperson does not respond or complete the survey, no additional spokespersons will be contacted. Approximately 2 weeks after the game event, players will be contacted by phone for a one-on-one interview.

Game piece examples:

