The WWYC smart-phone App will supplement the cards, dice, and spinner to provide a secure dynamic database for up to 6 players at a time. Once the game question for a given round has been selected, and each player has typed a response using their smart-phone, the App will display all responses, and allow players to guess which player gave which response. The App will keep track of players' scores (reflecting the number of correct guesses), as well as point totals. Because the App is also intended to promote engagement with spokespersons, the App will allow players to invite their spokesperson to participate. Through the App, participants will share a link with their spokesperson via text message.

Research staff coordinating the game event will visually confirm participants have forwarded this survey to their potential spokesperson. By clicking the link, the spokesperson will view the Summary Explanation of Research, confirm willingness to participate, and provide basic demographic information through REDCap. Should this spokesperson not respond after seven days, the player may forward the survey invitation link to an alternative spokesperson. Should the alternate not respond, no additional invitations will be sent. Upon leaving the event, participants will be given a formal healthcare power of attorney form to complete. Additionally, ~2 weeks after the event, the research team will contact participants by phone to conduct follow-up interviews.

Post-Game Outcomes Measured:

- Experience/process of game-play (i.e., one-on-one interviews, focus groups)
- Net Promoter Score
- Stage of Readiness to Choose a Spokesperson
- Choosing a Spokesperson
- Spokespersons' Engagement with Online Interface
- Player Evaluation

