## 8 Subject Numbers and Statistical Plan

### 8.2 Number of Subjects

Up to 800 participants (400 players and 400 spokespersons, with each game consisting of 4 players each)

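### Planned safety collection covers only players at game events, so distress in spokespersons, or in players afterwards, is not systematically collected

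*Combined protocol and SAP*

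**What the plan says.** Four short entries in Section 9 of the combined protocol and SAP define safety collection:

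- Under 9.2, game events are monitored for adverse reactions to the game, which is described as the sole intervention.
- Under 9.3, what is reviewed is limited to "Adverse reactions (e.g. emotional distress) experienced by player participants".
- Under 9.4, the only method listed is "Direct observation".
- Under 9.5, this happens at each game event.

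Section 9.7 has the cumulative data reviewed quarterly. Section 9.9 stops the game pending reassessment if it routinely causes distress.

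Spokespersons have their own eligibility criteria (3.1, 3.2) and consent within REDCap (5.2.1). Their task, in 7.1, is an online survey "asking what medical preferences they think the player would want in various clinical scenarios". The Duration of Participation section allows 15 to 20 minutes for it.

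For players, the Game Play text says that about 2 weeks after the event "the research team will contact participants by phone to conduct follow-up interviews".

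**The concern.** The safety plan is narrower than the set of people and activities in the study. Two things fall outside it.

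- **Spokespersons.** They are not at the event, so observation does not reach them, and 9.3 is worded for players only. The game rounds that staff observe use questions deliberately kept away from medical care (Game Play). The spokesperson's task is to predict which treatments someone who chose them would want, and it is done remotely. Section 10 expects people uneasy with the topic to select themselves out. That fits volunteers who answer an advertisement better than people nominated by a player and invited by text, although the latter may decline.
- **Players after the event.** Under 7.1, a first spokesperson's non-response is established only after a week, and an alternate may then be invited. Any reaction to that comes after the roughly 2-hour event.

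At stake is the completeness of what the quarterly review sees, and whether the team learns of people who need support. Section 15.5 offers support to any participant distressed by study activities, but Section 9 gives no active way of learning of such cases outside the event. No efficacy or feasibility estimate is affected.

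**Working it through.** **Step 1. Reproduce the plan's figure.** Sections 1.2 and 8.2 both give 400 players and 400 spokespersons: 400 + 400 = 800, as stated.

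**Step 2. Share of participants outside planned collection.** At the planned maximum, 400 / 800 = 50%.

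Spokespersons may not all enrol. If a fraction e of players has an enrolled spokesperson, the spokesperson share of everyone enrolled is e / (1 + e):

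| e | Spokespersons / all enrolled (400 players) | Share |
|---|---|---|
| 1.00 (planned maximum) | 400 / 800 | 50.0% |
| 0.75 (Aim 2 engagement threshold, used here as an assumption) | 300 / 700 | 42.9% |
| 0.50 (assumed lower case) | 200 / 600 | 33.3% |

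The share does not depend on the number of players. With the 100 players named in Aim 2 and e = 0.75, it is 75 / 175 = 42.9% again.

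**Step 3. Set planned safety collection against planned contact.**

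| Group and period | Contact already planned | Safety collection planned in Section 9 |
|---|---|---|
| Players, at the event (about 2 hours) | Game, questionnaires, focus group | Direct observation |
| Players, event to about 2 weeks | Phone interview at the end of the period | None stated |
| Spokespersons, during the survey | REDCap survey, 15 to 20 minutes | None stated |

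**Step 4. Look for other routes.**

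- Section 18.2 commits the investigator to report to the IRB harm that is observed or reported, in a subject or anyone else, if considered unexpected and probably related. This covers spokespersons and has no time limit, but it depends on someone coming forward.
- The 2-week interview reaches players and explores their experience of the game. The text does not say that it asks about distress or that its content goes to the safety review.
- Section 15.5 describes the response to distress, not how it is found.

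These routes exist, but they are incidental. None is listed as a source for the quarterly review in 9.7.

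**The case against.** The strongest reply is that the monitoring is matched to the risk. Section 10 calls this a minimal-risk study, and the game is its only intervention. Everyone who plays is observed at every event. The suspension provision in 9.9 concerns distress caused by the game, and spokespersons do not play it. Safety is not an endpoint (1.2, 1.3), a feasibility criterion in Aim 2 or a listed post-game outcome, so no planned result is biased. Spokespersons read a summary of the research and confirm willingness before answering. The survey, interview guide and summary are not shown, and may already give a contact route or ask about distress.

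Much of this stands, and it rules out three stronger readings that a reader might infer:

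- *That distress in spokespersons, or later distress in players, cannot be detected.* Section 18.2 covers reported harm in any subject, and the 2-week interview could bring late distress to light.
- *That half of the participants have no safety capture, so the review must see zero spokesperson events.* They have no solicited capture described in Section 9. Reported harms still count, and 50% is the planned maximum.
- *That a statement about the game's safety would rest on only half of those exposed.* Everyone who plays is observed at the event. For immediate reactions to the game, the suspension provision is matched to its data.

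The reply does not remove the gap itself. Sections 9.3 to 9.5 name one group, one method and one occasion, while 15.5 takes in all participants and all study activities. Content in an instrument that is not shown would not by itself bring those data within 9.3 or into the quarterly review.

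**Conclusion.** The point holds as a gap in systematic collection. As written, the quarterly review has no planned input from spokespersons (50% of participants at the planned maximum, about 43% if 75% of players have an enrolled spokesperson) and none from players after the event. Distress in either setting would reach the team only incidentally.

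This rests on reading 9.2 to 9.5 as the full statement of what is collected for safety, and on the 2-week interview and the spokesperson survey not being used for this purpose under some instrument that is not shown. The documents give no expected rate of distress in either group, so no number of missed cases can be derived. Distress from a spokesperson's non-response is a plausible example, not something the protocol reports.

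Importance is modest: minimal risk, no effect on any planned estimate, and a remedy that uses existing contacts. It is worth making as a cheap improvement.

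**What to change.** Extend 9.3 to 9.5 to both participant types and to the period after the event, using contacts already planned:

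1. Add one question to the 2-week player call on distress since the event.
2. Add one closing question on distress to the spokesperson REDCap survey. Give a study contact route there if the survey or the Summary Explanation of Research does not already do so. The route also serves anyone who stops before the last question. The text shown mentions only basic demographics being taken from spokespersons besides the survey answers, so follow-up may depend on the respondent making contact.
3. State in 9.7 that both sources enter the quarterly review, with the number asked and the number answering in each group, so that no reports can be told apart from no answers.

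The support arrangements in 15.5 and the suspension provision in 9.9 can stay as written.

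The cost is one question in an existing call, one in an existing survey, and matching wording in Section 9. No visits or staff are added. The downside is some follow-up of positive answers. Players not reached by phone and spokespersons who never finish the survey would still be covered only by spontaneous report.

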### 9.5 Frequency of data collection

Every game event

### 9.6 Individuals reviewing the data

PIs and data safety monitor ([name])

### 9.7 Frequency of review of cumulative data

Quarterly

### 9.8 Statistical tests

Not applicable.

## **9.9 Suspension of research**

In the unlikely event that the game intervention routinely provokes emotional distress, the game will be stopped pending reassessment by the study PIs and data safety monitor ([name]).

## **10 Risks**

This is a minimal risk study. It is possible that some individuals may experience emotional distress, however we suspect that individuals with a negative predisposition toward difficult conversations about surrogate decision-making will self-select to not participate in this research.

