To address these gaps, we have developed a novel intervention that includes a “serious game” to help people consider the qualities they want in their spokesperson, then engage the person they choose for this role. Combining a serious topic with an enjoyable activity (“gamification”) has been effective at changing health related behaviors in multiple settings with our target population (“sandwich generation” and older adults). The game element of our intervention, “*Who Would You Choose: Serious Fun*” (**WWYC**), prompts players (using scenarios and metaphors) to choose a spokesperson whose qualities are best suited to the role. At the end of the game, players identify a real-life spokesperson based on the qualities considered during gameplay. Then, using an online interface, WWYC will spark communication between the player and their chosen spokesperson. The long-term goal of this project is to help people make more thoughtful and informed choices when selecting a spokesperson, and to help these spokespersons be better prepared for their role as surrogate decision-makers. The current mixed methods study proposed here is designed to learn whether and how WWYC helps individuals select an appropriate spokesperson for healthcare decisions, as assessed via three **Specific Aims**:

**Aim 1 (QUALITATIVE):** To explore how playing a novel game affects people's choice of a spokesperson. Qualitative focus groups will be used to examine the group experience playing WWYC. One-on-one interviews will be used to explore how the game affected individual players' thought process for choosing a spokesperson, and whether that choice changed as a result of game-play.

**Aim 2 (QUANTITATIVE):** To establish that WWYC is a feasible way to help individuals choose and engage a spokesperson. We will judge WWYC as feasible if:

- We can efficiently recruit 100 individuals to play the game;
- $\geq 75\%$  of game players report that playing the game is helpful for choosing a spokesperson;
- $\geq 75\%$  of game players endorse the game, as measured by the Net Promoter Score;
- $\geq 75\%$  of spokespersons engage with WWYC (using its online interface) following player request

**Aim 3 (CONVERGENT MIXED METHODS):** To integrate qualitative and quantitative data via a joint display to explain how the experience of playing WWYC relates to their spokesperson's willingness to

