#### **4.2.3 When potential subjects will be recruited.**

August 2021 to June 2023

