#### **4.2.4 Describe the eligibility screening process and indicate whether the screening process will occur before or after obtaining informed consent. Screening begins when the investigator obtains information about or from a prospective participant in order to determine their**

**eligibility. In some studies, these procedures may not take place unless HIPAA Authorization is obtained OR a waiver of HIPAA Authorization when applicable for the screening procedures is approved by the IRB.**

Interested participants will be informed about the study and screened for eligibility during that initial conversation (in person, via telephone, email or Zoom). Names, phone numbers, or emails will only be used for screening or scheduling purposes and will not be linked to Participant ID or data.

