### 8.3 Sample size determination

Using purposive sampling, aim to recruit 50% female and >25% ethnic/racial minority participants. As a feasibility study, the main objective is to establish viability of the intervention rather than efficacy. Thus a power analysis is not necessary. The sample size reflects the number of participants we expect to be able to recruit in this time period to obtain the information necessary to answer study questions.

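### Aim 2 asks whether 100 players are recruited efficiently, but the plan counts nobody who enquires and declines, so only the number enrolled is tested

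*Combined protocol and SAP*

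**What the plan says.** Section 1.1 lists four feasibility criteria under Aim 2. Three are proportions with a threshold of 75%. The other concerns recruitment: "We can efficiently recruit 100 individuals to play the game". No rate, deadline, uptake level or cost limit is attached to efficiency there or elsewhere in the visible text.

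Section 4.2.3 gives the recruitment window as "August 2021 to June 2023". Section 8.3 states that "The sample size reflects the number of participants we expect to be able to recruit in this time period", without showing a rate. Section 15.3 records only an expectation that enough people will be found.

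Under Section 4.2.4, people who show interest are informed and screened in one conversation. Of the details taken, it says "Names, phone numbers, or emails will only be used for screening or scheduling purposes", and that they are not linked to study data. No log is described. Section 5.2.1 places players' consent later, at the game event. Neither the post-game outcomes in Section 7.2 nor the methods in Section 8.4 include numbers eligible, declining or attending.

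Section 10, on the risk of emotional distress, suspects that "individuals with a negative predisposition toward difficult conversations about surrogate decision-making will self-select to not participate in this research". Section 3.2 also excludes anyone who will not forward the survey to a possible spokesperson.

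The player numbers differ. Aim 2 uses 100. Section 1.2 has "Successful completion of data collection of 800 participants (400 players and 400 spokespersons" as the primary endpoint. Section 8.2 gives a ceiling: "Up to 800 participants (400 players and 400 spokespersons, with each game consisting of 4 players each".

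**The concern.** A feasibility criterion should be able to separate an intervention that people take up from one that most decline. Here the word that carries that meaning has no data behind it. If staff follow the plan as written, the report can say that 100 or more people played, but not what share of eligible enquirers agreed, why others declined, or how many were scheduled and did not come. Declines that are not noted when they happen are hard to recover afterwards.

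This affects the other three criteria too. Helpfulness, endorsement and spokesperson engagement are all measured among people who agreed to play, or through them. The protocol itself expects attitude to the topic to influence who agrees, and its eligibility rules add a filter on willingness to contact a spokesperson. Without uptake, a reader who sees 75% cannot judge how selected those players were. Section 1.1 presents the study as preparation for a randomised trial, and Section 2.1 calls for an intervention that appeals and can be scaled up. Acceptance among enquirers bears on both.

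**Working it through.** **Inputs**
- Recruitment criterion: 100 players (Section 1.1, Aim 2).
- Window: August 2021 to June 2023 (Section 4.2.3), counted inclusively: 5 + 12 + 6 = 23 months.
- Larger player number: 400 (Sections 1.2 and 8.2).
- Number of eligible people who enquire: not in the documents. Assumed range 125 to 1,000, for illustration only.

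**Figure to reproduce.** None. The plan states no recruitment rate, uptake or power.

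**Can the criterion fail on the count?** Yes. If the Section 4.2.3 window is taken as the deadline, 99 players by the end of June 2023 would miss it.

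**Can it fail on pace?** Pace = players / months.
- 100 / 23 = 4.3 players a month.
- 400 / 23 = 17.4 players a month.

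These differ by a factor of 4. Either gives at least 100 players within the window, and nothing says which would count as efficient.

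**Can it fail on uptake?** Uptake p = 100 / N, where N is the number eligible. The Wilson 95% interval, with z = 1.96, is

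[p + z²/(2N) ± z √(p(1 − p)/N + z²/(4N²))] / (1 + z²/N).

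For N = 125 the centre is (0.8 + 3.8416/250) / (1 + 3.8416/125) = 0.791. The half-width is 1.96 × √(0.00128 + 0.0000615) / 1.0307 = 0.070. The interval is therefore 72% to 86%. The other rows use the same formula.

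| N eligible (assumed) | Uptake | 95% CI | Criterion as written |
|---|---|---|---|
| 125 | 80% | 72 to 86% | 100 reached |
| 200 | 50% | 43 to 57% | 100 reached |
| 400 | 25% | 21 to 29% | 100 reached |
| 1,000 | 10% | 8 to 12% | 100 reached |

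**Effect on reading the 75% criteria.** Suppose exactly 75 of 100 players find the game helpful. They are 75/125 = 60% of the eligible in the first row and 75/1,000 = 7.5% in the last. These are only the shares known to be favourable; the views of those who declined are unknown. The reported 75% is the same in both cases.

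**The case against.** Several points on the other side are sound.

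- A reader might infer that the recruitment criterion cannot fail. That is wrong. It has a count, Section 4.2.3 gives dates, and a shortfall is possible. Only the efficiency part is untestable.
- A reader might infer that uptake can never be reported. That does not follow. Section 4.2.4 restricts the use and linking of contact details, not counting, and the screening conversation is a natural place for a tally. The separate data plan form cited in Section 22 is not among the documents and may describe a log. The supportable statement is that the visible plan specifies none.
- A reader might take Section 10 to rest participant safety on averse people staying away. It voices a suspicion. Sections 9.2 to 9.9 provide observation at every event, quarterly review and a suspension rule, and Section 15.5 provides support.
- The most substantial objection is that a tally captures only part of the selection. Recruitment is by advertisement, flier, social media and word of mouth (Sections 4.1 and 4.2.1). Many people who dislike the topic will never make contact. Uptake among enquirers could be high even if most of the public would refuse. Purposive sampling (Section 8.3) and the $50 gift card (Section 13) also affect it. This limits what the figure means, but a limited figure is still more than the plan now provides.
- The uptake values are hypothetical. They show that the criterion does not respond to uptake, not that uptake will be low.

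**Conclusion.** The concern holds in a limited form. Efficiency of recruitment is named as a feasibility criterion, but the visible plan collects nothing that measures it. The criterion tests whether 100 players are enrolled, presumably by June 2023, and no more. Over the assumed range of 125 to 1,000 eligible enquirers, uptake runs from 80% to 10% with the same result. Because the protocol itself suspects non-random opting out, the 75% criteria describe a willing group whose selectivity will be unknown.

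The absence of any planned count rests on the documents supplied, without the data plan form. The uptake range is an assumption, and the intervals treat people as independent.

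The documents do not support a particular deadline. It is tempting to spread 400 players evenly over 23 months and ask for 100 within about six (100 / 17.4 = 5.75 months). But 400 is a ceiling in Section 8.2, Aim 2 asks for 100, and nothing says that accrual is steady. If 100 is the operative target, 4.3 players a month is on schedule, and such a deadline would call it a failure.

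**What to change.** 1. **Section 4.2.4.** Keep an identifier-free tally of everyone who makes contact: informed, eligible, declining (with reason, separating topic from logistics), attending and consenting. Since consent is taken at the event, record non-attendance separately from refusal. Also count separately those found ineligible because they will not forward the survey; otherwise that form of refusal drops out of the denominator.
2. **Section 8.4.** Report consented over eligible with a 95% confidence interval, and the monthly recruitment rate, beside the recruitment criterion. State that uptake refers to people who enquired, because open advertising leaves the number reached unknown.
3. **Aim 2 and Section 8.4.** State that the 75% results apply to people willing to take part at the observed uptake.
4. **Sections 1.1, 1.2 and 8.2.** Reconcile the player numbers of 100 and 400. Any deadline or rate that defines efficient recruitment is then for the sponsor to set in advance.

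The cost is a tally sheet for staff and a few sentences. The downside for the sponsor is that the uptake figure may be unfavourable.
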